6.1.1 Serious Adverse Event Collection and Reporting

Following the subject's written consent to participate in the study, all SAEs, whether related or not related to study drug, must be collected, including those thought to be associated with protocol-specified procedures. All SAEs must be collected that occur within 30 days of discontinuation of dosing or within 30 days of the last visit for screen failures. The investigator should collect any SAE occurring after these time periods that is believed to be related to study drug or protocol-specified procedure.

An SAE report should be completed for any event where doubt exists regarding its status of seriousness.

If the investigator believes that an SAE is not related to study drug, but is potentially related to the conditions of the study (such as withdrawal of previous therapy, or a complication of a study procedure), the relationship should be specified in the narrative section of the SAE form.

SAEs must be recorded in the eCRF, pregnancies on a Pregnancy Surveillance Form. SAEs, whether related or not related to study drug, and pregnancies must be reported to ICON Clinical Research within 24 hours, by entering the SAE into the eCRF or Pregnancy Surveillance Form.

In the rare event that the Oracle Clinical Remote Data Capture (OC RDC) system is offline and a patient experiences a Serious Adverse Event, the site will call the **ICON SAE hotline** numbers and complete the 2 part SAE form and fax to **ICON Medical Affairs within 24-hours** using the **ICON Medical Affairs** and **Drug Safety SAE Fax Number** provided in the **BMS Contact Information List.**

In the event that the ICON Medical Monitor/Contact cannot be reached, the alternate BMS contact is:

Bristol-Myers Squibb Medical Monitor:

Office:

Fax:

If only limited information is initially available, follow-up reports are required. (Note: Follow-up SAE reports should include the same investigator term(s) initially reported.). All original paper SAE Forms (if used) and Pregnancy Surveillance Forms are to remain on site.

If an ongoing SAE changes in its intensity or relationship to study drug or if new information becomes available, a follow-up SAE eCRF should be completed within 24 hours and reported to ICON using the same procedure used for transmitting the initial SAE.

All SAEs should be followed to resolution or stabilization.

6.2 Nonserious Adverse Events

A nonserious adverse event is an AE not classified as serious.

6.2.1 Nonserious Adverse Event Collection and Reporting

The collection of nonserious AE information should begin at initiation of study drug. Nonserious AE information should also be collected from the start of a placebo lead-in period or other observational period intended to establish a baseline status for the subjects.

Nonserious AEs should be followed to resolution or stabilization, or reported as SAEs if they become serious (see Section 6.1.1). Follow-up is also required for nonserious AEs that cause interruption or discontinuation of study drug, or those that are present at the end of study treatment as appropriate. All identified nonserious AEs must be recorded and described on the nonserious AE page of the eCRF.

Completion of supplemental eCRFs may be requested for AEs and/or laboratory abnormalities that are reported/identified during the course of the study.

6.3 Laboratory Test Abnormalities

The following laboratory abnormalities should be captured on the nonserious AE eCRF page or SAE Electronic Case Report Form as appropriate:

- Any laboratory test result that is clinically significant or meets the definition of an SAE
- Any laboratory abnormality that required the subject to have study drug discontinued or interrupted
- Any laboratory abnormality that required the subject to receive specific corrective therapy.

It is expected that wherever possible, the clinical, rather than the laboratory term would be used by the reporting investigator (eg, anemia versus low hemoglobin value).

6.4 Pregnancy

If, following initiation of the investigational product, it is subsequently discovered that a study subject or a female partner of a male study participant is pregnant or may have been

pregnant at the time of investigational product exposure, including during at least 6 half-lives after product administration, the investigational product will be permanently discontinued for the female study participant in an appropriate manner (eg, dose tapering if necessary for subject safety). Protocol-required procedures for study discontinuation and follow-up must be performed on the subject unless contraindicated by pregnancy (eg, x-ray studies). Other appropriate pregnancy follow-up procedures should be considered if indicated.

The investigator must immediately notify the Medical Monitor of this event and complete a Pregnancy Surveillance Form within 24 hours and in accordance with SAE reporting procedures described in Section 6.1.1.

Follow-up information regarding the course of the pregnancy, including perinatal and neonatal outcome and, where applicable, offspring information must be reported on the Pregnancy Surveillance Form.

Any pregnancy that occurs in a female partner of a male study participant should be reported to the sponsor. Information on this pregnancy will be collected on the Pregnancy Surveillance Form

6.5 Overdose

An overdose is defined as the accidental or intentional ingestion or infusion of any dose of a product that is considered both excessive and medically important. All occurrences of overdose must be reported as SAEs (see Section 6.1.1 for reporting details).

6.6 Other Safety Considerations

Any significant worsening noted during interim or final physical examinations, electrocardiograms, x-rays, and any other potential safety assessments, whether or not these procedures are required by the protocol, should also be recorded as a nonserious or serious AE, as appropriate, and reported accordingly.

7 DATA MONITORING COMMITTEE AND OTHER EXTERNAL COMMITTEES

Refer to section 5.3.3

8 STATISTICAL CONSIDERATIONS

8.1 Sample Size Determination

The co-primary endpoints are the change in seated systolic blood pressure from baseline at Week 12 and the change in HbA1c at Week 12, or the last post-baseline measurement prior to Week 12, if no Week 12 assessment is available.

The first primary objective is to compare the differences in mean change between each dapagliflozin (2.5 mg, 5 mg and 10 mg) treatment group and the placebo treatment group in seated systolic blood pressure. With 262 subjects per treatment group with post-baseline measurements, there is at least 90% power to detect a difference of 4.5 mmHg in mean change from baseline in seated systolic blood pressure between each (2.5 mg, 5 mg and 10 mg) dapagliflozin treatment group and placebo treatment group at significance level of 0.017, assuming a standard deviation (SD) of 14 mmHg. If the result for the first primary endpoint is significant then a test for the second primary endpoint will be conducted. With 262 subjects per treatment group with post-baseline measurements, there is at least 96% power to detect a difference of 0.4% in mean change from baseline in HbA1c between each dapagliflozin (2.5 mg, 5 mg and 10 mg) treatment group and the placebo treatment group at significance level of 0.017, assuming a SD of 1.1%. Overall, with 262 subjects per treatment group, there is at least 86% power to detect 1 dapagliflozin treatment group that meets both co-primary endpoints with overall Type I error controlled at the 0.05 significance level (using Bonferroni's adjustment).

The primary comparisons are between each of the dapagliflozin (2.5 mg, 5 mg and 10 mg) treatment groups and the placebo treatment group. Each comparison between the dapagliflozin treatment group and placebo treatment group will be performed at the two-sided 0.017 level, using Bonferroni's adjustment so the family-wise Type I error rate is controlled at the 0.05 significance level.

Assuming 5% of the subjects do not have a post-baseline assessment, a total of 1104 subjects (276 subjects for each dapagliflozin treatment group and placebo treatment group) need to be randomized.

8.2 Populations for Analyses

Two efficacy data sets are specified for this study:

- The primary efficacy data set will consist of all randomized subjects who receive at least one dose of double-blind study medication. In addition, randomized subjects must have both a baseline and at least one post-baseline measurement for the time point under consideration to be included in the efficacy analysis of change from baseline.
- The secondary efficacy data set is a subset of the primary data set excluding primary efficacy variable data which may have been affected by protocol deviations as determined by the Medical Monitor. All decisions to exclude data from the primary data set will be made prior to the unblinding of the study.

The co-primary efficacy variables of change from baseline in seated systolic blood pressure and change from baseline in HbA1c will be reanalyzed using the secondary efficacy data set only if more than 10% of the subjects in any regimen are found to significantly violate the terms and conditions of the protocol. Otherwise, efficacy analysis will be restricted to the primary efficacy data set.

Safety analysis will be based on the safety data set which consists of all subjects who received at least one dose of study medication.

8.3 Endpoint Definitions

The co-primary endpoints are the change in seated systolic blood pressure and the change in HbA1c from baseline at Week 12, or the last post-baseline measurement prior to Week 12, if no Week 12 assessment is available. For subjects rescued for hypertension, measurements obtained after initiation of rescue medication will not be considered in calculating the co-primary endpoint of seated systolic blood pressure.

The secondary endpoints include the change in 24 hour ambulatory systolic blood pressure from baseline at Week 12, or the last post-baseline measurement prior to Week 12, if no Week 12 assessment is available, the change in seated and 24 hour ambulatory diastolic blood pressure from baseline at Week 12, or the last post-baseline measurement prior to Week 12, if no Week 12 assessment is available and the change in serum uric acid from baseline at Week 12, or the last post-baseline measurement prior to Week 12, if no Week 12 assessment is available. For subjects rescued for hypertension, measurements obtained after initiation of rescue medication will not be considered in calculating the secondary endpoints of 24 hour ambulatory systolic blood pressure and seated and 24 hour ambulatory diastolic blood pressure.

8.4 Analyses

8.4.1 Demographics and Baseline Characteristics

Frequency distributions and summary statistics for demographic and baseline variables summarized in efficacy analyses, will be computed by treatment group as well as for all subjects combined. No statistical test will be carried out for comparison of any baseline measurement among the treatment groups.

8.4.2 Efficacy Analyses

Unless otherwise specified, for all changes from baseline to a specific time point post-baseline, analyses will be based on measurements available at that time point or the last post-baseline measurement prior to that time point, if no measurement is available at that time point, ie, last observation carried forward (LOCF). For subjects who started anti-hypertensive rescue medication on the day of, or prior to, the specific time point, their last post-baseline measurement prior to the time and date of the first dose of rescue medication will be used for analyses of all blood pressure measurements.

8.4.2.1 Primary Analysis

The co-primary efficacy analysis will compare the change in seated systolic blood pressure from baseline at Week 12 and change in HbA1c from baseline at Week 12 for each dapagliflozin (2.5 mg, 5 mg and 10 mg) treatment group and the placebo treatment

group. The primary analysis will be conducted using a hierarchical testing procedure to maintain the overall 0.05 significance level.

The first primary analysis for the change in seated systolic blood pressure from baseline at Week 12 will be based on an analysis of covariance (ANCOVA) model with treatment group as the effect and baseline seated systolic blood pressure value and randomization strata as the covariates. Point estimates and 95% confidence intervals for the mean change within each treatment group as well as for the differences in mean change between each dapagliflozin (2.5 mg, 5 mg and 10 mg) treatment group and placebo treatment group will be estimated. P-values will be calculated to compare the treatment effect in each of the dapagliflozin (2.5 mg, 5 mg and 10 mg) treatment groups to that in the placebo treatment group. Each treatment group comparison will be performed at the two-sided 0.017 significance level, using Bonferroni's adjustment so the family-wise Type I error rate is controlled at the 0.05 significance level.

If the result for the first primary endpoint is significant then a test for the second primary endpoint will be conducted. The second primary analysis for the change in HbA1c from baseline at Week 12 will be based on an ANCOVA model with treatment group as the effect and baseline HbA1c value and randomization strata as the covariates. Point estimates and 95% confidence intervals for the mean change within each treatment group as well as for the differences in mean change between each dapagliflozin (2.5 mg, 5 mg and 10 mg) treatment group and placebo treatment group will be estimated. If the first primary endpoint for a treatment group was significant at the 0.017 significance level then p-values will be calculated to compare the treatment effect in that dapagliflozin treatment group to that in the placebo treatment group for the second primary endpoint. Each treatment group comparison will be performed at the two-sided 0.017 significance level, using Bonferroni's adjustment so the family-wise Type I error rate is controlled at the 0.05 significance level.

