Prior to randomization (first dose of double-blind study medication), the following criteria **MUST** be met:

- Subjects must have inadequately controlled hypertension, defined as SBP ≥ 140 and < 165 mmHg AND DBP ≥ 85 and < 105 mmHg, each representing the mean of three consecutive determinations, evaluated at both the enrollment and Day 1 visits.
- All non-central laboratory-related selection criteria evaluated at the enrollment visit
 have been met and have continued to be met throughout the lead-in period, and up to

the randomization visit. Central laboratory values that meet selection criteria at the enrollment visit are not required to meet the selection criteria at the entry into lead-in Day -28 visit. However, in the event of new laboratory abnormalities noted at the entry into lead-in Day -28 visit, the Investigator should ensure that they do not represent new and significant comorbidity that would preclude safe participation in the protocol. Such cases should be discussed with the medical monitor.

- No clinical conditions or clinically significant abnormalities, in any laboratory value(s) collected after enrollment and prior to randomization and/or ECG, which, in the Investigator's judgment, should preclude entry into the treatment period.
- Subjects should demonstrate good compliance with the administration of study medication (≥ 70% and ≤ 130%) during the lead-in period. For subjects with a compliance between ≥ 70% AND < 80% or > 120% AND ≤ 130%, the Investigator should ensure that there are no systematic factors that may result in unacceptable compliance with study medication during the treatment period of the trial. Such cases should be discussed with the Medical Monitor prior to randomization.
- Subjects should demonstrate the ability to perform SMBG as required per protocol (see Section 5.3.1).
- The total daily dose of commercially available OAD medication has remained stable since the enrollment visit.
- The total daily dose of commercially available ACEI or ARB and an additional antihypertensive medication has remained stable since the enrollment visit.

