5 STUDY ASSESSMENTS AND PROCEDURES

5.1 Flow Chart/Time and Events Schedule

Table 5.1A: Flow Chart for Protocol MB102077 - Qualification, Lead - in, Double Blind Treatment, and Follow - up Periods.

Procedure	Qualification Period	Les	Lead-in Period 12 Week Double Blind Treatment Period						Follow -up	Notes	
	Enrollment	Day -28	Day - 14	*Day	Day 1	Wk 2	Wk 4	Wk 8	Wk 12	Wk 13	*Day -1 visit may be performed between Day -7 and Day -1
Eligibility Assessments											
Obtain Informed consent	X										
Review Medical History	X				X						
Review Inclusion/Exclusion Criteria	X										
Review Randomization Criteria					X						
General Procedures											
Brief Physical Examination	X						X	X		X	See 5.3.5
Complete Physical Examination		X			X				X		See 5.3.5
Body Weight	X	X		X	X	X	X	X	X	X	

Table 5.1A: Flow Chart for Protocol MB102077 - Qualification, Lead - in, Double Blind Treatment, and Follow - up Periods.

Procedure	Qualification Period	Lead-in Period			12 W	eek Dou	ıble Blir Period	nd Treat	tment	Follow -up	Notes
	Enrollment	Day -28	Day - 14	*Day -1	Day 1	Wk 2	Wk 4	Wk 8	Wk 12	Wk 13	*Day -1 visit may be performed between Day -7 and Day -1
Seated Blood Pressure/ Heart rate	X	X	X	X	X	X	X	X	X	X	Seated blood pressure must be taken in 3 replicate measurements. See section 5.3.6
Orthostatic BP and Heart Rate					X				X		Orthostatic B/P must be taken after seated B/P and must be supine and standing.

Table 5.1A: Flow Chart for Protocol MB102077 - Qualification, Lead - in, Double Blind Treatment, and Follow - up Periods.

Procedure	Qualification Period	Lea	ad-in Po	eriod	12 W	eek Dou	ıble Blir Period	nd Treat	tment	Follow -up	Notes
	Enrollment	Day -28	Day - 14	*Day -1	Day 1	Wk 2	Wk 4	Wk 8	Wk 12	Wk 13	*Day -1 visit may be performed between Day -7 and Day -1
24-hr Ambulatory Blood Pressure Monitoring (ABPM)				X					х		Baseline 24-hr ABPM will be done between days -7 and -1. Week 12, 24-hr ABPM will be done within 1 week prior to the Week 12 visit. Note: If a subject needs rescue for hypertension the ABPM must be done prior to administration of the first dose of rescue medication and will be the last ABPM measurement for the study.
12-Lead ECG	X				X				X		
Height	X										
Body Mass Index (BMI)	X										

Table 5.1A: Flow Chart for Protocol MB102077 - Qualification, Lead - in, Double Blind Treatment, and Follow - up Periods.

Procedure	Qualification Period	Lea	Lead-in Period 12 Week Double Blind Treatment Period					Follow -up	Notes		

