This amendment further expands the existing procedures for the ongoing review of hepatic laboratory tests and hepatic events. Additional hepatic laboratory monitoring was implemented across the program in 2009 using the Food and Drug Administration (FDA) *Guidance for Industry, Drug-Induced Liver Injury: Premarketing Clinical Evaluation* (July 2009) as a reference. This amendment now incorporates ongoing external blinded review of specific hepatic laboratory tests and hepatic events. Bristol-Myers Squibb (BMS) and AstraZeneca (AZ) will request the opinions of independent hepatologists to determine the probability that drug-induced liver injury (DILI) is the cause of liver-related abnormalities.

Changes to the Protocol:

1) Synopsis, Study Design, Study Population and Investigational Product(s), Dose and Mode of Administration, Duration of Treatment with Investigational Product(s), Synopsis - Primary Objective, and Protocol Sections 1.3.1, 1.3.2, 1.3.3, 4.1.1, 5.4.1, 5.4.2, and 5.4.3: Deletion of the 2.5 dapagliflozin arm due to study design change. Also deletion of extra "mg" in the schematic, added "central" to alpha adrenergic agonist to synopsis and Protocol Section 1.1 Rationale, Section 3.1 Study Design, Section 3.1.1, Qualification Period, Section 3.1.2 Lead-In Period, Section 3.1.3, Double-Blind Treatment Period, Section 3.3.1 Inclusion Criteria #3, Section 4.1.2 Non Investigational Product and Section 3.5.1 Guidelines for the Addition of a Supplemental Antihypertensive Medication to Control Sustained or Severe

- Hypertension. Added words "effective therapeutic" to dose of ACEI or ARB. Design changed from 4 arm to 3 arms. Updated randomized subjects to 765 (255 dapagliflozin 5 mg, 255 dapagliflozin 10 mg and 255 placebo). Updated recruitment period to 9 months and study conducted over 13 months.
- 2) Synopsis, Study Schematic and Protocol Section 3.1.5 Study Schematic. Added Day -14 to schematic. Deletion of 2.5 dapagliflozin dose arm.
- 3) Synopsis, Study Population and Protocol Section 3.1 Study Design and Section 3.1.2 Lead-In period, Section 3.3.1 Inclusion criteria #5, Section 3.3.2 Randomization criteria, Section 5.4.2.1 24-hr Ambulatory Blood Pressure (ABPM). Added randomization criteria: Subjects must have a mean 24-hour blood pressure ≥ 130/80 mmHg as measured by ambulatory blood pressure monitoring (ABPM) during lead in, measured between Day -7 and Day -1, within 1 week prior to the Day 1 randomization visit.

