In line with the NAS 2010 recommendations for missing data report, the primary efficacy analysis will be a longitudinal repeated measures analysis using direct likelihood instead of using ANCOVA model based on the last observation carried forward (LOCF). The LOCF based analysis will be included as a sensitivity analysis. The details of the analysis will be described in the Statistical Analysis Plan.

Additionally, this amendment will decrease the minimum number of subjects to be randomized in the study. A total of at least 408 subjects (204 subjects each in the dapagliflozin 10 mg and placebo treatment groups) need to be randomized into the MB102077 study. Assuming 5% of the subjects do not have a post-baseline assessment, the study will have at least 80% power to detect a difference of 4 mmHg in mean change from baseline in seated systolic blood pressure between the dapagliflozin 10 mg treatment group and placebo treatment group at significance level of 0.05, assuming a standard deviation (SD) of 14 mmHg and at least 94% power to detect a difference of 0.4% in mean change from baseline in HbA1c between the dapagliflozin 10 mg treatment group and the placebo treatment group at significance level of 0.05, assuming a SD of 1.1%.

This amendment also removes Section 5.3.5 Guidance on Assessment of Cancer Cases. This section was added in amendment 8 with the expectation that there would be a change in the way cancer cases were evaluated across the dapagliflozin clinical trial program. However, while additional information has been collected and consultation with oncology experts has occurred for some specific cancer cases, a cancer adjudication

committee was not established for this trial. All cancer cases will be adjudicated in a separate large dapagliflozin cardiovascular outcomes trial.

This amendment will also include clarification on the appropriate use and monitoring of insulin as a background medication during the study.

Lastly, the amendment will correct the below listed typographical errors in the protocol, include minor clarifications as well as administrative changes.

This amendment has no impact on the study conduct or subject's safety. There is no urgency with the implementation of this amendment and it will apply to all subjects in all countries once approved.

Changes to the Protocol:

- 1) Cover page: Central Medical Monitor, Change in name of BMS Medical Monitor and contact details.

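### The shown seated-SBP model leaves out lead-in seated SBP and baseline 24-hour ambulatory SBP, which are already collected; pre-specifying them is a low-cost efficiency gain of uncertain size, not a correction of an error

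*Supplement*

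**What the plan says.** **Model.** Section 8.4.2.1 of the protocol describes the first primary analysis as an "analysis of covariance (ANCOVA) model with treatment group as the effect and baseline seated systolic blood pressure value and randomization strata as the covariates". The Amendment 09 rationale replaces this: "the primary efficacy analysis will be a longitudinal repeated measures analysis using direct likelihood instead of using ANCOVA model based on the last observation" (the LOCF approach). It adds: "The LOCF based analysis will be included as a sensitivity analysis". On specifics it says: "The details of the analysis will be described in the Statistical Analysis Plan". The Amendment 09 change list records Section 8.4.2.1 as revised for the new method and mentions no new blood pressure covariate. Amendment 08 had added insulin use as a stratification factor. Neither the revised section nor the SAP is among the documents.

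**Data available before randomization.** Table 5.1A schedules seated blood pressure at enrollment, Day -28, Day -14, Day -1 and Day 1, with the note "Seated blood pressure must be taken in 3 replicate measurements". Section 3.1.2 requires an adequate 24-hour ambulatory recording between Day -7 and Day -1. Amendment 02 made its result a randomization criterion: "Subjects must have a mean 24-hour blood pressure ≥ 130/80 mmHg as measured by ambulatory blood pressure monitoring (ABPM) during lead in".

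**Entry window.** The randomization criteria in Section 3.3.2 set SBP at 140 to <165 mmHg, "each representing the mean of three consecutive determinations, evaluated at both the enrollment and Day 1 visits".

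**Size.** Amendment 09: "A total of at least 408 subjects (204 subjects each in the dapagliflozin 10 mg and placebo treatment groups) need to be randomized". It assumes that 5% have no post-baseline value and states at least 80% power for 4 mmHg with SD 14 mmHg at the 0.05 level.

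**The concern.** Every randomized subject has a Day 1 SBP within a 25 mmHg band. A covariate from one visit, truncated in this way, carries limited information about a subject's usual pressure and so explains little of the variation at Week 12. The lead-in seated readings and the ambulatory mean carry more of that information. They precede randomization and will be on the database for nearly everyone. Used as pre-specified covariates, they reduce residual variance without meaningful bias.

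SBP is where precision matters most. In the text shown, HbA1c is tested only after SBP succeeds (Section 8.4.2.1), and the secondary endpoints only after both (Section 8.4.2.2). Amendment 09 reduced the study from 722 to at least 408 subjects and sized the SBP comparison at about 80%.

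**Working it through.** **1. Reproduce the plan's figure.** Inputs from Amendment 09: 204 per arm, 5% without a post-baseline value, difference 4 mmHg, SD 14 mmHg, alpha 0.05 (taken as two-sided).

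- Evaluable per arm: 0.95 × 204 = 193.8, about 194.
- Standard error: 14 × √(2/194) = 1.421 mmHg.
- Power = Φ(4/1.421 − 1.960) = Φ(0.854) = 80.3%, which agrees with at least 80%.

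**2. Convert a variance reduction into power.** Let R² be the share of the variance remaining after Day 1 SBP that the added covariates explain. Taking 14 mmHg as the SD after adjustment for Day 1 SBP, the new SD is 14 × √(1 − R²). The equivalent number of extra randomized subjects is 408/(1 − R²) − 408.

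| R² | SD (mmHg) | Power | Equivalent extra subjects |
|---|---|---|---|
| 0.03 | 13.79 | 81.5% | 13 |
| 0.07 | 13.50 | 83.1% | 31 |
| 0.09 | 13.36 | 83.9% | 40 |
| 0.20 | 12.52 | 88.2% | 102 |

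Over a deliberately wide R² range of 0.02 to 0.30, the gain runs from 0.8 to 11.6 points.

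**3. Find a plausible R².** The documents give no visit-to-visit SD, correlation or R², so these are assumptions. One simulation generated a true pressure per subject (mean 148 mmHg), independent visit noise, and a person-level drift to Week 12 (SD 6 mmHg). It applied 140 to <165 at enrollment and Day 1 only. The added covariates were the enrollment and lead-in seated readings and ambulatory SBP.

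| Between-person SD | Visit SD | R² | Power |
|---|---|---|---|
| 8 | 12 | 0.082 | 83.6% |
| 10 | 12 | 0.111 | 84.7% |
| 10 | 10 | 0.129 | 85.4% |
| 12 | 9 | 0.158 | 86.6% |
| 14 | 8 | 0.173 | 87.2% |

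Here the ambulatory value added only 0.002-0.014 to R²; the repeat seated readings did nearly all the work. Across between-person SD 8-14 and visit SD 8-12.5 mmHg, further runs put the reduction at about 7-20%.

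**4. Repeat with the window held throughout lead-in.** If 140 to <165 also applies at Day -28, Day -14 and Day -1, the lead-in readings are truncated too. The combined reduction falls to about 3-9%, with power of about 82-84%. In one such run the lead-in mean alone gave about 1-4%, and about 4-7% with ambulatory SBP. Under this reading the ambulatory value is a larger part of a smaller gain.

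**5. Which SD is 14 mmHg?** Amendment 09 gives it beside the mean change from baseline and does not say whether it is before or after adjustment. In the step 3 simulation, adjusting for Day 1 SBP took the SD of change from 12.01 to 11.63 in one scenario and from 15.55 to 14.70 in another. Scaling 14 by those ratios gives 13.56 and 13.23 mmHg, hence 82.8% and 84.5% power before any covariate is added. Another set of assumptions put this starting power at about 84-88%.

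**The case against.** **The ANCOVA is superseded, and covariates are normally left to the SAP.** This stands in part. A reader might infer that the current primary model omits these readings. The documents do not support that: the revised Section 8.4.2.1 and the SAP are not shown. What can be said is that the only covariate set shown omits them and that no later change log adds them. The request is therefore to pre-specify or confirm.

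**Baseline plus strata is conventional and valid.** This stands. A reader might infer that the trial is underpowered or the analysis defective. The stated power is met without the change, 408 is a minimum, and if 14 mmHg is the unadjusted SD of change, power already exceeds 80%. Nor does the shown model adjust for baseline SBP alone, since it includes the randomization strata.

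**Lead-in visits may share the entry window.** This stands as an ambiguity. The Section 3.3.2 randomization criteria require non-laboratory criteria met at enrollment to continue to be met throughout lead-in. Section 3.1.2 gives Day -14 only a discontinuation limit of >180/110 mmHg, and inclusion criterion 4 names Day -1 where the randomization criteria name Day 1. These passages need reconciling. The direction of the gain is the same under either reading; its size is not.

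**No single gain can be derived.** This stands. A fixed number of power points would rest on variance components that the documents do not supply.

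**Conclusion.** The point holds as an efficiency improvement. The shown SBP model uses one range-restricted baseline reading plus the strata, while further prognostic readings taken before randomization go unused. With between-person SD 8-14 and visit SD 8-12.5 mmHg, both assumed, and 14 mmHg read as the SD after adjustment for Day 1 SBP, power rises from about 80% to about 83-88% without a lead-in window, or to about 82-84% with one. If 14 mmHg is the unadjusted SD, the proportional variance reduction is unchanged but the starting power is higher and the gain in points smaller. Confidence is good on direction and cost. It is limited on size, and the current model's covariates cannot be confirmed from these documents.

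**What to change.** Before unblinding, state in Section 8.4.2.1 and the SAP, or confirm if already there, that the repeated-measures model for seated SBP includes:

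- Day 1 seated SBP;
- the mean of the Day -28, Day -14 and Day -1 seated SBP readings, with a rule for a missing reading;
- optionally, baseline 24-hour ambulatory SBP, whose added gain is smaller if lead-in visits have no window;
- all randomization strata, including insulin use from Amendment 08.

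Also state whether the SD of 14 mmHg is before or after baseline adjustment, and reconcile the passages on whether the SBP window applies during lead-in.

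The cost is a line or two of wording and no new data. The model gains two parameters in about 390 subjects (2 × 194 = 388), or eight if both covariates interact with the four post-baseline visits (2 × 4).
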